3.0 Project Procedures

This will be a randomized pragmatic study for all patients ages 6-17 years with simple lacerations. Simple lacerations will be defined as lacerations within the scope of pediatric emergency medicine providers AND not requiring sedation or operative intervention. Subjects will be identified by the Emergency Department staff for enrollment. The goal number of enrolled participants will be 480, including 240 patients randomized into two groups, 120 per group, and 240 parents/guardians. The Emergency Department accepted to participate in this study and ED providers will complete the provider's survey. After signing the consent and assent form when appropriate, the patients will be randomized to either receive the standard of care or standard of care with immersive virtual reality goggles. Consent and assent will be obtained in the patient rooms within the emergency department. The standard of care shall be defined to include any of the following: local analgesia (topical LET and/ or subcutaneous lidocaine), oral or intranasal midazolam, distraction, Child Life Staff, or physical holding. Because each of the aforementioned interventions may vary between patients, it cannot be truly standardized; hence, this will be considered a pragmatic study. Patients randomized to the VR arm will receive the other standard procedures as well with VR goggles as an adjunct. Exclusion criteria include a history of epilepsy, visual or hearing impairment, or intellectual disability that would preclude use of VR goggles as determined by the guardian. Additionally, any lacerations around the eyes, eyebrows, and nose will be excluded as well as patients requiring sedation. Non-English speaking patients will be excluded as well. Hand lacerations will not be excluded.

Participants will be identified by ED staff following evaluation of the laceration. The ED staff will be given a flowchart with eligibility criteria. All interested participants who meet eligibility criteria will be consented. A research team member will obtain consent from parents or guardians by providing and reviewing the consent form (see Subject Consent Form). For patients who are between 8 and 17 years of age, a research team member will obtain assent by providing and reviewing the assent form (see Subject Assent Form). Consent and assent will be obtained in the patient's ED room.

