Patients will be separated into groups age 6-11 and 12-17. Patients will be randomized via a selection of a sealed envelope which will contain instructions for use of the VR goggles. The goggles utilized will be Lenovo Mirage Solo with DayDream, which are standalone VR headset with WorldSense Body Tracking. Research staff will coach the child on age-appropriate games, as previously determined by Lenovo.

The goggles will be cleansed with Oxivir Tb disinfectant wipes after each use and allowed to dry in room air prior to next use. Education will be provided to all ED providers on the proper cleansing protocol for the VR goggles (Figure 4). The disinfectant protocol will be available for all users during the study, and has been approved by the director of Infection Control at Children's Hospital of the King's Daughters.

Following the laceration repair, the patient, guardian and health care provider will be surveyed (Figure 1, 2, and 3) on paper surveys. The survey includes Likert-type scale questions, binary

questions as well as incorporates the Wong Baker Faces Pain Scale and Children's Fear Scale. The duration of the procedure will be recorded by the healthcare provider who completed the laceration repair. Time of procedure will be defined as from the time of irrigation to wound dressing. Patients and parents will both be filling out their own individual surveys. The parent should complete the survey first before the child should the child need assistance with completion. Patients and parents may decline to participate in any survey at any time.

The recruitment period will be from November 2021 until February 2021. Enrolled participants will not be compensated, and enrollment will be completely voluntary.

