4.0 Statistical Analysis

Continuous variables will be presented as mean, standard deviation, median, 25th, and 75th percentile. Categorical variables will be presented as frequency and percentage. Generalized Linear Model (GLM) will be used to assess the effect of intervention on the outcomes of the surveys. The correlation between provider's, parent's, patient's survey will be analyzed using the Spearman's correlation test. All statistical tests will be performed using the R software. All statistical tests will be 2-sided and $p < 0.05$ will be considered as statistically significant.

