11. How would you rate the patient's pain:

Wong-Baker FACES® Pain Rating Scale

12. How would you rate the patient's fear:

No fear A little fear Some fear A lot of fear The most fear

Figure 3. Use of Immersive Virtual Reality for Laceration Repairs in the Pediatric Emergency
Department
Provider Survey

1. Procedure Duration (*from irrigation to closure end*):
A. <10 minutes
B. 10-15 minutes
C. 16-20 minutes
D. 21-25 minutes
E. >25 minutes

2. Did the patient use VR goggles for the procedure today?
 Yes
 No

3. Would you recommend VR goggles again for this procedure?
 Yes
 No

4. Did the patient need to be held during the procedure?
 Yes
 No

5. Did the patient receive medicine intended to help them stay calm?
 Yes
 No

6. During the procedure, did the patient experience any symptoms (select all that apply)?
 Did not experience any symptoms
 Dizziness
 Headache
 Nausea
 Vomiting
 Other (*describe below*)

7. How do you think the procedure went overall?
 Not well at all
 Somewhat not well
 Neutral
 Somewhat well
 Very well

8. In your opinion, did the virtual reality goggles make the procedure seem less scary to the patient?

Strongly disagree
 Disagree
 Neutral
 Agree
 Strongly agree

9. How would you rate the patient's pain:

10. How would you rate the patient's fear:

[figure not shown]

Figure 4. Education Plan for Disinfection Protocol for Virtual Reality Goggles

1. The company insert for cleansing the virtual reality goggles will be printed, laminated, and physically located with the goggles in their carrying case.
2. The protocol for cleaning will be addressed during an Emergency Medicine division meeting prior to the start of the project and detailed in the meeting minutes.
3. The protocol will be addressed during a pediatrics monthly resident meeting and dispersed in an email from the chief residents.
4. The protocol will be emailed to all rotating residents prior to the start of their rotation.
5. The protocol will also be disseminated to nursing staff and ED techs via [name] prior to the start of the project.
6. Research project staff will be available either in person or by phone to answer any questions regarding the disinfection protocol during the study phase of the project. Contact information will be included inside the carrying case for the goggles as well as on all written communications (division meeting minutes, chief email, etc.)

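### Procedure time is defined as irrigation to wound dressing, but the only duration item shown asks for irrigation to closure end, in five bins

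*Combined protocol and SAP*

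**What the plan says.** Section 2.0 lists time of procedure among the secondary outcomes. Section 3.0 defines the interval: "Time of procedure will be defined as from the time of irrigation to wound dressing". It assigns the recording to the person who did the repair: "The duration of the procedure will be recorded by the healthcare provider who completed the laceration repair". On the instrument, section 3.0 says that "ED providers will complete the provider's survey", and on timing: "Following the laceration repair, the patient, guardian and health care provider will be surveyed". These are paper surveys, shown as Figures 1 to 3.

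Item 1 of the provider survey (Figure 3) asks for procedure duration "from irrigation to closure end" and offers five boxes: under 10, 10-15, 16-20, 21-25 and over 25 minutes.

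Section 4.0 has a rule for each type of variable: "Continuous variables will be presented as mean, standard deviation, median, 25th, and 75th percentile" and "Categorical variables will be presented as frequency and percentage". It adds: "Generalized Linear Model (GLM) will be used to assess the effect of intervention on the outcomes of the surveys". It does not say which type procedure time is, and it gives no family or link for the model.

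**The concern.** One outcome has two stop points. A reader who relies on section 3.0 will take the reported time to include dressing the wound, while the form stops before that. Unless a record exists that the documents do not describe, the missing interval cannot be recovered once the forms are complete.

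The bins add a second limitation. A natural practical question is how many minutes the goggles add or save. Ticked boxes show a shift between categories. They give a difference in minutes only through a distributional assumption that the plan does not make. The top category has no upper limit, and the lowest, though bounded at zero, is wide.

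**Working it through.** **Text comparison.**

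| | Section 3.0 | Figure 3, item 1 |
|---|---|---|
| Start | irrigation | irrigation |
| Stop | wound dressing | end of closure |
| Scale | not stated | five categories |

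The patient and guardian surveys have no duration item. No form shown has a field for start time, stop time, dressing time or minutes. The item and its five options are fully legible, so text lost in conversion does not explain the mismatch.

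**Illustration of the cost of binning.** The plan states no figure for this outcome, so there is none to reproduce. From the documents: 120 per arm, two-sided 5% level, the five bins. Assumed: lognormal times, log-SD 0.5, ratio of times 0.83 (17% shorter), pooled median m, bin cuts at 10, 15.5, 20.5 and 25.5 minutes.

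1. *Choice of effect.* ln(0.83) / (0.5 × √(2/120)) = −0.1863 / 0.0645 = −2.89. With rank-test efficiency 0.955, 2.89 × √0.955 = 2.82, and Φ(2.82 − 1.96) ≈ 0.81. Simulation gives 0.80. The effect was chosen to give about 80% power on exact times.
2. *Bin shares.* The arm medians are m/√0.83 and m × √0.83. At m = 20 they are 21.95 and 18.22. The share above 25 minutes is the average of 1 − Φ(ln(25.5/21.95)/0.5) = 0.382 and 1 − Φ(ln(25.5/18.22)/0.5) = 0.251, that is 0.316.
3. *Power*, 40,000 simulated trials per median:

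| Pooled median (min) | 8 | 12 | 15 | 20 | 25 | 30 |
|---|---|---|---|---|---|---|
| Share under 10 min | 0.670 | 0.360 | 0.213 | 0.086 | 0.036 | 0.015 |
| Share over 25 min | 0.011 | 0.069 | 0.148 | 0.316 | 0.484 | 0.625 |
| Rank test, exact times | 0.802 | 0.801 | 0.804 | 0.803 | 0.801 | 0.803 |
| Rank test, five bins | 0.641 | 0.753 | 0.773 | 0.764 | 0.724 | 0.672 |
| Rank test, rounded to 5 min | 0.728 | 0.775 | 0.788 | 0.793 | 0.795 | 0.801 |
| t-test, log of times rounded to 5 min | 0.737 | 0.785 | 0.800 | 0.808 | 0.811 | 0.817 |

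At medians 12 to 25 the bins lose between 0.804 − 0.773 = 3 points and 0.801 − 0.724 = 8 points. At 8 and 30 they lose 16 and 13.

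4. *Minutes estimated from the bins.* At m = 20 the true mean difference is e^0.125 × (18.22 − 21.95) = −4.23 minutes. A lognormal model fitted to the binned data averages −4.15 when times are lognormal. If times are gamma with the same mean and coefficient of variation, it averages −4.67, and −4.67/−4.23 = 1.10, a 10% overstatement. At m = 25 it averages −6.17 against −5.29, or 17%. At 12 and 15 the error is a few percent at most (−2.51 against −2.54; −3.25 against −3.17; Monte Carlo SE 0.05 and 0.06). The answer in minutes thus depends on a shape that the bins may not settle.

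**The case against.** Only the stop point is a contradiction. The plan never promises a difference in minutes, and section 4.0 covers categorical variables, so the bins conflict with nothing. The power figures concern the bins, not the stop point. If an equal lag of 1 or 2 minutes from closure to dressing is added to both arms in the same model, power on the bins moves by at most about 2.5 points at medians 12 to 25, in either direction. The effect was back-solved, the plan does not propose the lognormal fit, and a survey filled in afterwards may yield only rounded minutes. A cut at 9.5 instead of 10 would put 32% and 19% below 10 minutes at medians 12 and 15, rather than 36% and 21%. Section 3.0 also does not confine the provider's recording to Figure 3.

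Much of this stands. An ordinal comparison between arms remains valid, and the cut at 9.5 barely changes power. The simulation is a scenario, not evidence about this trial. An undescribed record cannot be excluded. None of it removes the mismatch: followed as written, the form collects a different interval from the one defined. A 1-minute lag would move about 11% to 16% of patients up one category, so the reported percentages would shift even though the randomised comparison would not change much. The bins are a design choice, but an irreversible one: bins can be derived from minutes, not minutes from bins.

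**Conclusion.** The concern holds. The documented form does not collect this secondary outcome as section 3.0 defines it, and it cannot give a measured difference in minutes. That conclusion rests on the text alone.

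The consequence is moderate. The size of the end-point gap is unknown and may be small. It would bias the comparison only if the time from closure to dressing differed by arm, which is not expected. The loss of 3 to 8 points of power at medians 12 to 25, and the larger loss when many repairs fall in an end category, rest on the assumed lognormal shape, log-SD and effect. The change should be made, but neither the primary outcomes nor the validity of the trial depends on it.

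**What to change.** Choose one stop point and word it identically in section 3.0 and in Figure 3, item 1. Replace the boxes with start and stop times, or whole minutes. Analyse log(minutes) in the planned GLM and report the ratio of times with a 95% CI. Under the assumptions above, the limits are the ratio divided and multiplied by exp(1.97 × 0.5 × √(2/120)) = 1.14.

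If the bins are kept, still align the wording. Declare the outcome ordinal, report frequencies and percentages by arm, and specify a proportional-odds model. If forms have already been completed, report the interval actually asked for and use this ordinal analysis.

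The cost is one form item and one protocol sentence, with slightly more for the provider to write. If recall rounds every time to 5 minutes, the power gain over the bins is small in mid-range: about 1 to 3 points at medians 12 to 20 and 7 at 25 with a rank test on both. With the log(minutes) model it is 3 to 4 points and 9, of which about 2 come from the lognormal assumption. Noting clock times during the repair would reduce the rounding.

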2.0 Objectives

The objective of this study is to determine if VR goggles can decrease patient pain and anxiety during simple laceration repairs. The primary outcome will be pain scores as assessed by the validated Wong Baker Faces Scale and anxiety scores as assessed by the validated Children's Fear Scale. A validated System Usability Scale (SUS) will be measured for each enrolled participant that used the VR goggles. Secondary outcomes include time of procedure, use of physical holding, adverse outcomes, and pharmacologic interventions.

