6.0 Budget

The Virtual Reality goggles are property of the Children's Hospital of the King's Daughters Child Life department. They will be stored in a locked drawer within the CHKD Emergency Department. This project is unfunded.

Figure 1. Use of Immersive Virtual Reality for Laceration Repairs in the Pediatric Emergency
Department
Patient Survey

1. How old are you? _____

2. Have you had stitches before? Yes
 No
 Unsure

3. Have you ever used Virtual Reality (VR) goggles before today? Yes
 No
 Unsure

4. Did you use VR goggles for your stitches today? Yes
 No

5. Would you use VR goggles again to get stitches? Yes
 No

6. During your stitches, did you have any of the following (select all that apply)?
 I did not experience any symptoms
 Dizziness
 Headache
 Nausea
 Vomiting
 Other (describe below)

7. How do you think the stitches went overall? Not well at all
 Somewhat not well
 Neutral
 Somewhat well
 Very well

8. The virtual reality goggles made the stitches seem less scary.
 Strongly disagree
 Disagree
 Neutral
 Agree
 Strongly agree

9. How would you rate your pain:

10. How would you rate how scared you were during the stitches:

[figure not shown]

Figure 2. Use of Immersive Virtual Reality for Laceration Repairs in the Pediatric Emergency
Department
Guardian Survey

1. **Patient Gender:**

Male
 Female
 Non-binary
 Self-identify
 Prefer not to say

2. What is the patient's age? _____

3. Please indicate if the patient has a developmental disability:

A. The patient does not have a developmental disability
B. Autism
C. Cerebral Palsy
D. Intellectual disability
E. Speech delay
F. _____

4. Has the patient had stitches previously? _____

Yes
 No
 Unsure

5. Has the patient ever used Virtual Reality (VR) goggles before today? _____

Yes
 No
 Unsure

6. Did the patient use VR goggles for the procedure today? _____

Yes
 No

7. If, yes, would you use VR goggles again for this procedure? _____

Yes
 No
 Did not use today

8. During the procedure did the patient experience any symptoms (select all that apply)?

Did not experience any symptoms
 Dizziness
 Headache
 Nausea
 Vomiting
 Other (*describe below*)

9. How do you think the procedure went overall?

- Not well at all
- Somewhat not well
- Neutral
- Somewhat well
- Very well

10. In your opinion, did the virtual reality goggles make the procedure seem less scary to the patient?

[figure not shown]
- Strongly disagree
- Disagree
- Neutral
- Agree
- Strongly agree

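### Where a child needs help with the survey, an unblinded guardian who has already scored pain and fear may give it, so the child's score can drift towards the guardian's

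*Combined protocol and SAP*

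**What the plan says.** Section 2.0 defines the primary outcome by scale: "The primary outcome will be pain scores as assessed by the validated Wong Baker Faces Scale and anxiety scores", the latter on the Children's Fear Scale. It does not say whose rating counts.

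Three people use these scales. Section 3.0 states: "Following the laceration repair, the patient, guardian and health care provider will be surveyed". It continues: "Patients and parents will both be filling out their own individual surveys". The next sentence sets an order: "The parent should complete the survey first before the child should the child need assistance with completion". The helper is not named, and neither is the kind of help.

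The forms are printed as Figures 1 to 3.
- The child's form (Figure 1) asks at item 9 "How would you rate your pain" and at item 10 about fear. Item 4 asks whether the child used the goggles.
- The guardian's form (Figure 2) asks at item 11 "How would you rate the patient's pain" and at item 12 about fear. Item 6 asks "Did the patient use VR goggles for the procedure today". Item 10, directly before the pain and fear items, asks whether the goggles made the procedure less frightening.
- None of the three forms has an item on whether the child was helped, or by whom.

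Section 4.0 plans a generalized linear model (GLM) for the effect of the intervention on the survey outcomes. The association between the provider, parent and patient surveys is to be "analyzed using the Spearman's correlation test". Neither analysis mentions helped forms.

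**The concern.** Putting the guardian first keeps the guardian's rating free of the child's answers. It does nothing for the child's rating. When help is needed, the likeliest helper has already recorded a score on the same scales, knows the arm, and has just been asked whether the goggles made things less scary.

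Two analyses are exposed. The parent-child correlation may partly reflect help given rather than agreement reached separately. The arm comparison of the child's own pain and fear scores may take in some of the guardian's expectation.

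The plan itself foresees help, and enrolment starts at age 6. Because help is not recorded, its effect could not be examined once the data are in.

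**Working it through.** The plan gives no figure to reproduce here: it states no expected correlation, no share of helped children, and no effect size or standard deviation (SD). The only design figure used is 120 patients per arm (section 3.0). Everything else below is assumed and shown as a range.

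**Model.** A share *f* of children is helped. A helped child's recorded score is (1 − *w*) × own score + *w* × guardian's score, where *w* = 0 means no influence and *w* = 1 means full copying.

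**Effect on the correlation.** Child and guardian scores were simulated as bivariate normal (400,000 pairs), with assumed underlying correlations of 0.3 and 0.5. Without help, these give Spearman values of 0.29 and 0.48.

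| Share helped *f* | Shift *w* | From 0.29 | From 0.48 |
|---|---|---|---|
| 5-10% | 0.25-0.5 | 0.30-0.33 | 0.49-0.52 |
| 20-40% | 0.5-1 | 0.38-0.57 | 0.55-0.69 |

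The direction is upward in every case. The size runs from near negligible to material.

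**Effect on the arm comparison.** Let *b*G and *b*C be the arm-related reporting bias of guardian and child. Assume that *f* and *w* are the same in both arms and that both raters reflect the same true effect. Then:

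added bias = *f* × *w* × (*b*G − *b*C)

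- If the guardian leans towards VR by 1 point more than the child: 0.2 × 0.5 × 1 = 0.1 point, up to 0.4 × 1 × 1 = 0.4 point.
- If both lean equally: *f* × *w* × 0 = 0.
- If the guardian leans less than the child, the sign reverses and guardian help reduces the total bias.

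**Effect on the type I error.** Take 120 per arm, two-sided 0.05, and *b*G − *b*C = 0.3 SD. The standard error of the difference is √(2/120) = 0.129 SD. This counts only the bias added by help, with no true effect and no bias in the child's own reports.

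| *f* | *w* | Added bias | Type I error |
|---|---|---|---|
| 10% | 0.5 | 0.1 × 0.5 × 0.3 = 0.015 SD | 0.052 |
| 25% | 0.5 | 0.25 × 0.5 × 0.3 = 0.0375 SD | 0.060 |
| 50% | 1 | 0.5 × 1 × 0.3 = 0.15 SD | 0.213 |

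With no difference between the two biases, help leaves the type I error unchanged.

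**The case against.** The strongest reply is that the sentence is conditional and modest. It applies only if a child needs help, it follows a statement that each party fills in its own form, and it does not say that the guardian helps choose a score. Help could mean no more than reading or writing any of the ten items. The order also has a real benefit, since it protects the guardian's rating. The correlation is a single sentence in section 4.0 and is not an outcome in section 2.0. All of this stands, and it limits the point to what can happen with helped children.

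A reader might go further in three ways that the documents do not support.
- *The parent-child correlation is inflated.* The share helped and the degree of influence are not given. Nothing supports a floor of, say, 20% for ages 6 to 17, and at 5-10% helped the change can be trivial.
- *The primary outcome is contaminated.* Section 2.0 names scales and no rater. The child's self-report is the natural choice, but that is an inference.
- *The treatment comparison is biased towards VR by 0.1 to 0.4 points.* That figure sets the child's own bias to zero. The child knows the arm too, so the added bias may be zero or reversed.

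The reply does not answer why help goes unrecorded, or why no analysis looks at helped forms. It also does not explain the purpose of the ordering rule if the guardian is not a possible helper.

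**Conclusion.** The point holds as a cheap improvement. Following the plan as written can pull helped children's ratings towards those of an unblinded guardian who has already scored. This rests on reading the guardian as a possible helper, which the text implies but does not state.

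The parent-child correlation can rise by as little as 0.01 (0.29 to 0.30) or by as much as 0.28 (0.29 to 0.57) across the assumed ranges. Any added bias in the arm comparison has unknown size and direction. It would come on top of the bias already possible in an open-label self-report and would not be its only source. The documents do not support a statement that the trial's result is biased in favour of VR by this route.

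**What to change.** In section 3.0, replace the ordering sentence with: *The child gives the pain and fear ratings by pointing to the faces before seeing or discussing the guardian's ratings. Anyone who helps only reads the item aloud and marks the child's choice; where available this is a staff member rather than the guardian. The guardian completes a separate form without seeing the child's answers.* The last sentence keeps the protection that the present order gives the guardian's rating. Reversing the order alone would not be enough, because a guardian who helps first would still not give an independent rating.

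Add one tick box: *Child needed help: none / staff / guardian.*

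In section 2.0, state that the child's rating is the primary one.

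In section 4.0, report help by arm and by age group (6-11 and 12-17). Repeat both the GLM on the child's pain and fear scores and the parent-child Spearman correlation without guardian-helped forms. Keep these as sensitivity analyses, with all forms in the main analysis: help arises after randomization and may differ by arm, so the reduced set is not a fully randomized comparison.

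The cost is one form item, a few sentences, and about a minute for younger children. Staff help should be preferred, not required, because the plan does not place research staff in the room when surveys are completed and the project is unfunded. Research staff also coach the child on the games and know the arm, which is why the helper's role is limited to reading and marking.
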